8.2.2 Sensitivity Analysis

Not performed.

8.2.3 Technical Details of Key Secondary Efficacy Endpoint Analysis

The SAS code for examination of dose-response relationship is shown below.

```
proc glm data = DATA;  
  class TRTP;  
  model CHG = TRTP BASE;  
  contrast '1 mg saturated' TRTP 4 -1 -1 -1 -1;  
  contrast '2 mg saturated' TRTP 7 2 -3 -3 -3;  
  contrast '5 mg saturated' TRTP 9 4 -1 -6 -6;  
  contrast 'linear' TRTP 2 1 0 -1 -2;  
run;
```

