Primary Objective: To investigate the dose response in respect of weight decrease following repeated oral administration of OPC-131461 at 1, 2, 5, 10 mg or placebo in patients with CHF with volume overload despite having diuretics other than vasopressin antagonists.	Primary Efficacy Endpoint: Change in body weight from baseline to the last assessment time point (the day after investigational medicinal product [IMP] administration) by Day 8 Secondary Efficacy Endpoints: Change in body weight from baseline to the last assessment time point (the day after IMP administration) by Day 15 Percent change in body weight from baseline to the last assessment time point (the day after IMP administration) by Day 8 Percent change in body weight from baseline to the last assessment time point (the day after IMP administration) by Day 15 Improvement of or change in congestive findings (lower limb edema, pulmonary congestion, jugular venous distention, hepatomegaly, cardiothoracic ratio, pulmonary rales, and cardiac third sound) from the baseline to the last assessment time point (the day of IMP administration) by Day 7 Improvement of or change in congestive findings (lower limb edema, pulmonary congestion, jugular venous distention, hepatomegaly, cardiothoracic ratio, pulmonary rales, and cardiac third sound) from baseline to the last assessment (the day after IMP administration) by Day 15 Congestive findings (lower limb edema, pulmonary congestion, jugular venous distention, hepatomegaly, cardiothoracic ratio, pulmonary rales, and cardiac third sound), time to resolution of congestive findings, and the New York Heart Association (NYHA) Functional Classification

Table 2-1 Trial Objectives and Endpoints	
Objectives	Endpoints

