8.1.1 Primary Efficacy Endpoint Analysis

For the primary analysis, an analysis of covariance model with treatment group as a fixed effect and baseline body weight as a covariate will be used. The least squares mean and two-sided 95% confidence interval (t-distribution) of each dose group will be determined. In addition, the least squares mean difference between OPC-131461 dose groups and the placebo group and two-sided 95% CI (t-distribution) and p-value will be calculated by comparing those groups at a two-sided significance level of 5%. Control of experimental-wise type 1 error per test will not be performed.

Similar analysis will be performed using the primary analysis model excluding baseline body weight.

For the change from baseline in body weight at the last assessment, a bar graph of the least squares mean (two-sided 95% CI [t-distribution]) with the treatment group as the horizontal axis will be prepared for each model.

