8.2 Key Secondary Efficacy Endpoint

8.2.1 Key Secondary Efficacy Endpoint Analysis

For the key endpoint, in order to investigate the dose-response relationships for placebo, 1, 2, 5, and 10 mg, a model similar to that used in the primary analysis will be used to contrast the response saturated at 1 mg, response saturated at 2 mg, response saturated at 5 mg, and linear response.

Similar analysis will be performed using the primary analysis model excluding baseline body weight.

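### Does the contrast labelled linear in SAP 8.2.3 need changing because it is coded on dose rank rather than on mg?

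*SAP*

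**What the plan says.** The primary objective in Table 2-1 is "To investigate the dose response in respect of weight decrease" over placebo and 1, 2, 5 and 10 mg. Section 8.2.1 plans a set of contrasts "to investigate the dose-response relationships for placebo, 1, 2, 5, and 10 mg". The shapes are saturation at 1 mg, saturation at 2 mg, and "response saturated at 5 mg, and linear response". The text does not say whether linear refers to mg, log dose or the order of the dose groups.

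Section 8.2.3 gives the code. The two contrasts whose coefficients depend on the dose scale are "contrast 'linear' TRTP 2 1 0 -1 -2" and "contrast '5 mg saturated' TRTP 9 4 -1 -6 -6". Section 8.3.1 applies the same analysis to Day 15.

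The contrasts do not stand alone. Section 8.1.1 states: "The least squares mean and two-sided 95% confidence interval (t-distribution) of each dose group will be determined". It adds the difference of each dose from placebo with its interval and p-value, and a bar graph "with the treatment group as the horizontal axis will be prepared for each model". It also says: "Control of experimental-wise type 1 error per test will not be performed".

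**The concern.** The doses are unevenly spaced, and the list in 8.2.1 is in mg, so a reader naturally takes linear to mean linear in mg. The code does something else: it gives each step between neighbouring doses the same weight, so the step from 5 to 10 mg counts no more than the step from placebo to 1 mg. A results table with a line labelled linear and a small p-value might then be read as a response that keeps rising in proportion to dose up to 10 mg.

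Dose response is the primary objective. The sample size in section 4 assumes that 5 mg and above match the reference drug's effect, so whether the response levels off from 5 mg is a question the trial should inform. If the label misled on that point, the conclusion about dose would be affected. The coded linear contrast is also close to the contrast for saturation at 5 mg, which makes the two hard to tell apart.

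**Working it through.** **Inputs.** Doses 0, 1, 2, 5, 10 mg (8.2.1); printed coefficients (8.2.3); 31 per group, SD 1.30 kg, difference 1.09 kg, two-sided 5% (section 4). Two assumptions are added: 1.09 kg is the largest effect in every shape, and the baseline covariate explains no variance.

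**1. Reproduce the coefficients.** Take scores, cap them at the named dose, subtract the mean, multiply by −5 (the sign is reversed because weight loss is negative).
- Ranks 0,1,2,3,4 (mean 2): 10, 5, 0, −5, −10, proportional to 2 1 0 −1 −2. Matches.
- Ranks capped at 5 mg, 0,1,2,3,3 (mean 1.8): 9 4 −1 −6 −6. Matches.
- On mg, 0,1,2,5,10 (mean 3.6): 18 13 8 −7 −32. Capped at 5 mg, 0,1,2,5,5 (mean 2.6): 13 8 3 −12 −12. Neither is the printed set.
- The 1 mg and 2 mg contrasts are the same on both scales.

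So the code follows one consistent rule, equal steps between dose levels.

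**2. Shape in mg.** The coded linear shape rises by 1, 1, 0.33 and 0.20 units per mg over 0–1, 1–2, 2–5 and 5–10 mg. At 5 mg it has reached 3/4 = 75% of its top value, against 5/10 = 50% on a mg line. Its correlations are:
- with the mg-linear contrast: 120/√(10×1630) = 0.940
- with the coded 5 mg contrast: 40/√(10×170) = 0.970
- with log(dose+1): 0.997

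Coding both contrasts in mg would still leave them correlated at 0.893.

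**3. Power.** Noncentral t with 155 − 6 = 149 df and ncp = Σcμ / (1.30·√(Σc²/31)). For the coded contrast the denominator is 1.30·√(10/31) = 0.738; for the mg version it is 1.30·√(1630/31) = 9.427. Example, response flat from 1 mg, coded contrast: 1.09×(−1+0+1+2)/0.738 = 2.18/0.738 = 2.95.

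| True shape | Coded: ncp, power | mg version: ncp, power |
|---|---|---|
| Flat from 1 mg | 2.95, 83.5% | 2.08, 54.3% |
| Saturated at 2 mg | 3.69, 95.6% | 2.83, 80.4% |
| Linear in mg up to 5 mg, then flat | 4.13, 98.4% | 3.84, 96.8% |
| Linear in mg | 3.54, 94.1% | 3.77, 96.3% |

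The coded contrast is often significant under every one of these shapes. The mg version behaves the same way to a lesser degree. The last row is the only direct cost of the coding to a test of a mg-linear trend: 96.3 − 94.1 = 2.2 points.

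**4. The four contrasts read together.** Simulated trials under the same assumptions (400,000 per shape):
- Flat from 1 mg: the 1 mg contrast is the largest in about 84% of trials, the linear one in about 2%.
- Linear in mg: the linear contrast is the largest in 93%.
- Linear in mg up to 5 mg, then flat: the 5 mg contrast is the largest in 50% and the linear one in 46%, so these two are poorly separated.

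**5. Would adding mg-coded contrasts help?** With six contrasts instead of four, a 5 mg contrast is the largest in 72% rather than 50% when the response is linear in mg up to a 5 mg plateau. A linear contrast is the largest in 84.5% rather than 93% when the truth is linear in mg, and in 54% rather than 65% when it is linear in log dose. All of this assumes that the largest contrast is taken as the shape, a rule the SAP does not set.

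**The case for a change.** The strongest case for a change is that it would cost almost nothing. Those who read the results see the label, not the code, and the methods text in 8.2.1 leaves the scale open. One clause stating that linear means equal steps between dose levels, with a reminder that one significant contrast does not settle the shape, would remove the risk on the trial's primary objective. The SAP gives no rule for reading the four contrasts together, and the bar graph by treatment group does not show a dose scale either.

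Much of this stands as fact. The scale is not put into words, the linear label is loose, and significance of that contrast does not show linearity in mg. What does not follow is a fault in the analysis. Two programmers working from 8.2.3 would run identical tests. The proposed wording alters no coefficient, estimate or p-value. The high rates of significance under saturation come largely from the fact that any monotone trend contrast responds to any monotone effect, as the mg-coded figures show, so they are only in part evidence about the scale. For the 5 mg contrast the label is accurate as it stands: its coefficients are flat from 5 mg, and the label claims nothing about spacing below that dose.

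**Conclusion.** No change to the plan is needed. The coded linear contrast is linear in dose rank and close to linear in log(dose+1), a reasonable choice for doses of 1, 2, 5 and 10 mg. It is fully specified and valid as a trend test, and it loses about 2 points of power (94.1% against 96.3%) if the response is truly linear in mg. The SAP does not claim that its significance proves linearity. The least squares means by dose, with their intervals and differences from placebo, let a reader see directly whether the response flattens.

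The missing scale is a gap in wording that the printed coefficients fill, and stating it when results are reported is ordinary practice. Replacing the contrast with a mg-coded one, or adding mg-coded ones, would be a trade-off with mixed results: better at detecting a mg-scale plateau at 5 mg, worse at recognising a mg-linear or log-linear response. Adding them would also put more correlated tests, at Day 8 and again at Day 15, into a plan without multiplicity control.

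The figures rest on 31 per group, SD 1.30 kg, a maximum effect of 1.09 kg and no variance explained by baseline weight. Other effect sizes would move the percentages. The main reason for leaving the plan alone, that the tests are fixed by their printed coefficients, does not depend on them.

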8.3 Secondary Efficacy Endpoint Analyses

8.3.1 Body Weight

For the change in body weight from baseline (before IMP administration on Day 1) to the last assessment time point (the day after IMP administration) by Day 15, an analysis will be performed in the same manner as the primary endpoint analysis, and a bar graph will be prepared. The same analysis as described in [Section 8.2.1](#) will be performed.

For body weight at the last assessment by Day 8 (the day after IMP administration), the last assessment by Day 15 (the day after IMP administration), and each time point, descriptive statistics of the actual values, amount of change and percent change from the baseline will be calculated for each treatment group.

8.3.2 Lower Limb Edema, Pulmonary Congestion

For lower limb edema and pulmonary congestion, improvement rates (percentages of subjects who have symptoms at baseline and show markedly improved or improved after IMP administration [improvement grading is as per Table 8.3-1]) and resolution rates (percentages of subjects who have symptoms at baseline and no symptoms after IMP administration) at the last assessment time point (the day of IMP administration) by Day 7 and the last assessment time point (the day after IMP administration) by Day 15, and their two-sided 95% CIs (Clopper-Pearson) will be determined for each group.

Fisher's exact test will be used to compare each OPC-131461 dose group and the placebo group.

For time to improvement and time to resolution ("time to improvement/resolution or censoring" minus "starting point", the same applies hereinafter), Kaplan-Meier plots will be prepared by treatment group for subjects with symptoms at baseline to estimate the median and the two-sided 95% CI (log-log transformation). Day -1 will be used as the starting point, and if no events have occurred as of the day after the final IMP administration of the study drug, the study will be censored at that point.

For changes in the severity of symptoms, shift tables from baseline to the last assessment on Day 7 (day of IMP administration), the last assessment on Day 15 (the day after IMP administration) and each time point after IMP administration will be prepared for each treatment group.

The improvement rate at each time point after administration of the IMP will be calculated for each treatment group.

Table 8.3-1 Improvement Grading for Lower Limb Edema and Pulmonary Congestion		
	Improvement Grading	Criteria for Assessment
1	Markedly improved	Symptom resolution or improvement by at least 2 grades
2	Improved	Improvement by 1 grade (symptom resolution will be assessed as markedly improved)
3	Unchanged	No change in the severity of symptoms/no symptoms throughout the trial period
4	Worsened	Worsening by at least 1 grade

8.3.3 Pulmonary Rales, Cardiac Third Sound

For pulmonary rales and cardiac third sound, resolution rates (percentages of subjects who have symptoms at baseline and no symptoms after IMP administration) at the last assessment time point (the day of IMP administration) by Day 7 and the last assessment time point (the day after IMP administration) by Day 15, and their two-sided 95% CIs (Clopper-Pearson) will be determined for each group. Fisher's exact test will be used to compare each OPC-131461 dose group and the placebo group.

For the time to resolution, a Kaplan-Meier plot will be prepared for each treatment group in subjects with symptoms at baseline to estimate the median and two-sided 95% CI (log-log transformation). Day -1 will be used as the starting point, and if no events have occurred as of the day after the final IMP administration of the study drug, the study will be censored at that point.

For changes in the presence or absence of symptoms, shift tables from baseline to the last assessment on Day 7 (day of IMP administration), the last assessment on Day 15 (the day after IMP administration) and each time point after IMP administration will be prepared for each treatment group.

8.3.4 Jugular Venous Distention, Hepatomegaly, Cardiothoracic Ratio

For changes in jugular venous distension, hepatomegaly, and cardiothoracic ratio from baseline, an analysis of covariance will be performed using treatment group as a fixed effect and baseline value as a covariate, and the differences in the least squares means between each OPC-131461 dose group and the placebo group at the last assessment time point (the day of IMP administration) by Day 7 and the last assessment time point (the day after IMP administration) by Day 15, and the two-sided 95% CIs (t-distribution) will be determined. Similar analysis will be performed using a model excluding baseline values.

For the last assessment by Day 7 (the day of IMP administration), the last assessment by Day 15 (the day after IMP administration), and each time point, descriptive statistics of the actual values and amount of change from the baseline will be calculated for each treatment group. For changes in the presence or absence of jugular venous distention and hepatomegaly, shift tables from baseline to the last assessment on Day 7 (day of IMP administration), the last assessment on Day 15 (the day after IMP administration) and each time point after IMP administration will be prepared for each treatment group.

For the time to resolution of jugular venous distention and hepatomegaly, a Kaplan-Meier plot will be prepared for each treatment group in subjects with symptoms at baseline to estimate the median and two-sided 95% CI (log-log transformation). Day -1 will be used as the starting point, and if no events have occurred as of the day after the final IMP administration of the study drug, the study will be censored at that point.

8.3.5 NYHA Functional Classification

For the NYHA Functional Classification, the percentages of subjects who show improvement by at least 1 class from baseline at the last assessment time point (the day of IMP administration) by Day 7 and the last assessment time point (the day after IMP administration) by Day 15 among subjects classified as at least Class II, and their two-sided 95% CIs (Clopper-Pearson) will be determined for each group. Fisher's exact test will be used to compare each OPC-131461 dose group and the placebo group.

For changes in classification, shift tables from baseline to the last assessment on Day 7 (day of IMP administration), the last assessment on Day 15 (the day after IMP administration) and each time point after IMP administration will be prepared for each treatment group.

8.4 Subgroup Analyses

Subgroup analyses will be performed for the following stratification items in the main analysis of the primary endpoint. Similar analysis will be performed using the main analysis model excluding baseline body weight.

Table 8.4-1 **Stratification Item**

Table 8.4-1 Stratification Item	
Item	Level
Sex	Female, Male
Age	<65, >=65
NYHA Functional Classification	Class I, Class II, Class III and Class IV
Ischemic heart disease	Yes, No
Heart failure type	Right Heart Failure, Left Heart Failure, Bi-ventricular Failure
Loop diuretics	Loop diuretic alone, Loop diuretic + other diuretic
Loop diuretic dose (Furosemide equivalent)	< 40 mg/day, ≥ 40 to < 80 mg/day, ≥ 80 mg/day
Diuretic category *Concomitant use of diuretics other than loop diuretics, thiazide diuretics, or mineralocorticoid receptor antagonists will not be considered	Loop diuretic alone, Loop diuretic + thiazide diuretic, Loop diuretic + mineralocorticoid receptor antagonist, Loop diuretic + thiazide diuretic + mineralocorticoid receptor antagonist
Thiazide diuretic	No, Yes
Mineralocorticoid receptor antagonist	No, Yes
Daily urine volume (baseline)	<1500 mL, ≥1500 mL
Creatinine (baseline)	<2 mg/dL, ≥2 mg/dL
Plasma AVP concentration (baseline)	<=3.1 ng/L, >3.1 ng/L
Albumin (baseline)	<3 g/dL, ≥3 g/dL

9 Safety Analyses

The following analyses will be performed by treatment group (and by dose and overall for the OPC-131461 groups) on the safety analysis set.

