The results of the phase 3 confirmatory trial of tolvaptan (Protocol 156-06-002; placebo-controlled 7-day treatment) demonstrated that the change from baseline in body weight on the day after the final IMP administration (LOCF) was -0.45 ± 0.93 kg (mean \pm standard deviation [hereinafter, the same applies]) for the placebo group and -1.54 ± 1.61 kg for the tolvaptan 15-mg group. Based on these results, assuming a treatment difference of -1.09 , standard deviation (combined) of 1.30 , statistical power of 90% , and two-sided significance level of 5% , the sample size required is set as 31 subjects per group for a total of 155 subjects.

5 Statistical Analysis Datasets

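### The subgroup analyses of the primary endpoint repeat the main ANCOVA by level with no treatment-by-subgroup interaction, so the planned tables cannot show whether the effect differs between levels

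*SAP*

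**What the plan says.** Section 8.4 reads: "Subgroup analyses will be performed for the following stratification items in the main analysis of the primary endpoint". Table 8.4-1 then lists 14 items, and the section adds a repeat without baseline body weight. The main analysis is defined in section 8.1.1 as an ANCOVA with treatment group and baseline weight. It yields a least squares mean difference from placebo for each dose, a 95% CI and a test: "p-value will be calculated by comparing those groups at a two-sided significance level of 5" per cent. The code in section 8.1.3 has those two terms only. Section 8.1.1 also says "Control of experimental-wise type 1 error per test will not be performed".

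For subgroups, Appendix 1 lists one ANCOVA table (CT-5.7.1) and one further table (CT-5.7.2). The SAP contains no interaction term or test, no minimum level size or merging rule, and no statement on how the subgroup results are to be read.

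**The concern.** A subgroup analysis asks whether the drug effect differs between levels. That is a question about the treatment-by-subgroup interaction. A p-value within one level answers another question, namely whether a dose differs from placebo among those subjects, and the answer depends heavily on how many subjects the level holds. A significant result in one level beside a non-significant one in another is not evidence that the effects differ.

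At stake is how the subgroup tables are read. Items such as plasma AVP, creatinine and diuretic category could appear to separate responders from non-responders when only precision differs.

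**Working it through.** **Inputs.** From SAP section 4: "assuming a treatment difference of -1.09" kg, "standard deviation (combined) of 1.30" kg, "statistical power of 90" per cent, two-sided 5%, and "31 subjects per group for a total of 155 subjects". From section 8.1.1: four doses, each compared with placebo. From Table 8.4-1: the items and levels. The SAP does not give the number of subjects per level, so level sizes below are assumptions.

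**Reproducing the plan's sample size.** The normal approximation gives 2 × (1.960 + 1.282)² × 1.30² / 1.09² = 29.9, so 30 per group. With the noncentral t distribution, power is 89.1% at 30 and 90.1% at 31. The planned 31 is confirmed.

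**Counting.** In table order the levels are 2+2+4+2+3+2+3+4+2+2+2+2+2+2 = 34, or 33 if NYHA III and IV are one level. Multiplying by four doses gives 136 (or 132) comparisons per model. This is a ceiling, because an empty level yields none.

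**Power within a level, same true effect everywhere.** With m subjects per arm in a level and five arms, the noncentrality is 1.09 / (1.30 × √(2/m)) and the residual degrees of freedom are 5m − 6. The CI half-width is t × 1.30 × √(2/m).

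| Assumed m per arm | Noncentrality | df | Power | 95% CI half-width |
|---|---|---|---|---|
| 16 | 2.37 | 74 | 65% | 0.92 kg |
| 10 | 1.87 | 44 | 45% | 1.17 kg |
| 6 | 1.45 | 24 | 29% | 1.55 kg |
| 3 | 1.03 | 9 | 15% | 2.40 kg |

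Part of this does not depend on guessed sizes. The smallest level of a two-, three- or four-level item averages at most 31/2 = 15.5, 31/3 = 10.3 or 31/4 = 7.75 per arm. With an even spread over arms, power there is at most about 63%, 46% and 36%. Every item therefore contains at least one level well below the planned 90%.

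**Discordant levels without heterogeneity.** Take a two-level item split 16 and 15 per arm, with power 65% and 62%. For one dose, the chance that exactly one level is significant is 0.65 × 0.38 + 0.62 × 0.35 = 0.247 + 0.217 = 46%. A simulation of 1,500 trials used equal-sized levels, independent items, no covariate and a 1.09 kg effect in every level. On average about 31 of the 14 × 4 = 56 item-by-dose combinations were significant in some levels and not in others.

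**A separate scenario: no drug effect.** The expected number of nominally significant results is 136 × 0.05 = 6.8 per model (132 × 0.05 = 6.6 with 33 levels). The expectation needs no independence. This must not be added to the figures above, which assume the full effect.

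**What an interaction test could detect.** For one dose against placebo and a 50/50 split (15.5 per arm per level), the standard error of the difference in effects is 1.30 × √(2/15.5 + 2/15.5) = 0.660 kg. Power for a 1.09 kg difference in effect is Φ(1.09/0.660 − 1.96) = Φ(−0.31), about 38%. For 80% power the difference must be (1.96 + 0.84) × 0.660 = 1.85 kg. With an 80/20 split the figures are 26% and 2.31 kg.

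**Precision from pooling.** At 3 per arm, a separate fit gives 2.26 × 1.30 × √(2/3) = 2.40 kg. An all-subject model has a t multiplier near 1.98, giving 1.98 × 1.30 × √(2/3) = 2.10 kg.

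**The case against.** Several points on the other side stand.

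- Separate fitting within levels is a reading. Section 8.4 shows no subgroup code and does not itself mention p-values. It remains the natural reading, because the section invokes the main analysis and that analysis includes them.
- The SAP bases no dose or population decision on subgroups and openly leaves type 1 error uncontrolled.
- Per-level differences with 95% CIs already come with the main analysis, so that part of the output is not new.
- The interaction tests are weak. A single test per item spans four doses, so it has 4 degrees of freedom for a two-level item and 12 for a four-level one, and is less focused than the one-dose case calculated above.

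A reader might infer that apparent subgroup differences will mostly be chance. The SAP does not support that forecast, since it gives neither level sizes nor any information on true heterogeneity. Ten of the 14 items have two levels, so each has one level with at least half the subjects. A reader might also double the count to include the repeat without baseline weight. That repeat tests the same contrasts on the same subjects, and several diuretic items overlap, so a doubled total would overstate the problem.

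None of this supplies the missing comparison between levels. Disclosing that multiplicity is uncontrolled does not make within-level tests answer the heterogeneity question.

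**Conclusion.** The concern holds in a limited form: the method named in section 8.4 does not address whether effects differ between levels. On the natural reading it yields up to 136 (132) within-level p-values per model. With a homogeneous effect of the planned size and the assumed level sizes, these have roughly 15% to 65% power each, so mixed significance is the expected pattern even when nothing differs. The figures rest on the SAP's own effect and SD, an even spread over arms, and level sizes that are assumptions. They do not show that any particular subgroup finding will be false. The primary result is unaffected. This is a cheap improvement to the analysis of a secondary question.

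**What to change.** Reword section 8.4 before unblinding:

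- For each item, fit one ANCOVA on all subjects with treatment, subgroup, treatment-by-subgroup and baseline body weight.
- Report dose-placebo differences per level with 95% CIs and one interaction p-value per item, without within-level p-values.
- Label the results exploratory.
- State that levels too sparse to estimate will be merged or only described, and say whether NYHA III and IV are one level.

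This leaves 14 tests per model in place of up to 136, with 14 × 0.05 = 0.7 nominal positives expected if no interaction exists. Keeping the repeat without baseline weight is optional, since the SAP uses that paired layout elsewhere.

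The cost is SAP wording and a revised layout for CT-5.7.1; no new data are needed. The drawback is the low interaction power shown above: a non-significant interaction must not be read as evidence of a uniform effect, and the CIs should carry the interpretation.
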